### **9.5 Other Assessments**

#### **9.5.1 Number and Size of Follicles during Stimulation**

For each subject, the number of follicles on stimulation day 1 and last day of stimulation will be summarized for the mITT and ES cohorts. The summary will include the following:

1. the number of subjects that have follicles of size <10 mm, 10 mm, 11 mm, 12 mm, 13 mm, 14 mm, 15 mm, 16 mm, and  $\geq 17$  mm,
2. a summary of the number of follicles  $\geq 17$  mm (the count for each subject will be summarized across subjects),
3. the number of subjects that have at least two follicles that are  $\geq 17$  mm, and
4. a summary of the percentage of follicles  $\geq 17$  mm,  $\geq 15$  mm, and  $\geq 12$  mm (for each subject the percentage will be first derived and this subject level summary will be summarized across subject using mean, SD, etc.).

#### **9.5.2 E2 and Progesterone Profiles**

The central laboratory E2 and progesterone profiles will be summarized for mITT and ES cohorts, using descriptive statistics by scheduled visit, as well as for the change from screening for post-screening visits.

For patients in the mITT population, the local laboratory E2 assessments will be summarized by visit.

#### **9.5.3 Oocytes**

For each subject, the number of oocytes retrieved, the number of germinal vesicle, metaphase I, metaphase II and Degenerated oocytes will be summarized by frequency distribution and by descriptive statistics for the mITT and ES cohorts.

#### **9.5.4 Characterization of Fertilized Oocytes one Day (Day 1) after Oocyte Retrieval**

The status of fertilized oocytes will be summarized 1 day after oocyte retrieval for the mITT and ES cohorts. The summary will be both at the subject level and at the oocyte level.

For the summary at the subject level, for each subject, the percentage of fertilized oocytes with pronuclei 2 pn will be derived. The percentage will be derived over the number of oocytes retrieved. These percentage will further be summarized using descriptive statistics (i.e., mean, SD, etc.). The percentage of fertilized oocytes with continue destiny will be similarly analyzed.

For the fertilized oocyte level summary, the number and percentage of fertilized oocytes falling in each category of pronuclei will be presented (i.e., > 2 pn, 2 pn, 1 pn, 0 pn and damaged). The percentage derivation will be over the total number of oocytes classified.

These summaries will be obtained for mITT and ES cohorts.

#### **9.5.5 Quality of Blastocysts 5 Days (Day 5) after Oocyte Retrieval**

The quality of blastocysts 5 days after oocyte retrieval will be assessed at both the blastocyst level and at the subject level. The evaluation of fertilized oocytes at Day 5 will consist of assessment of embryo stage and classification of blastocysts according to blastocyst expansion and hatching status, blastocyst inner cell mass grading and trophectoderm grading. Furthermore, the destiny of the embryo will be recorded.

Embryo stage is classified as blastocyst, morula, degenerated or cleavage stage. For embryos still at the cleavage stage the number of blastomeres will be recorded.

Destiny at Day 5 is either transferred, cryopreserved or out of trial.

The scoring of blastocysts is based on the classification system by Gardner & Schoolcraft.

Blastocyst expansion and hatching status will be assessed as one of the following:

1. An early blastocyst, blastocoel being less than half volume of that of the embryo
2. A blastocyst with a blastocoel whose volume is half of, or greater than half of, that of the embryo
3. A blastocyst with a blastocoel completely filling the embryo
4. An expanded blastocyst with a blastocoel volume larger than that of the early embryo, with a thinning zona
5. A hatching blastocyst with the trophectoderm starting to herniate through the zona
6. A hatched blastocyst, in which the blastocyst has completely escaped from the zona

For blastocysts with expansion and hatching status on Day 5, blastocyst inner cell mass grading and trophectoderm grading will be evaluated.

Blastocyst inner cell mass grading will be assessed as one of the following:

- A. Tightly packed, many cells
- B. Loosely grouped, several cells
- C. Very few cells

Trophectoderm grading will be assessed as one of the following:

- A. Many cells forming a cohesive epithelium
- B. Few cells forming a loose epithelium
- C. Very few, large cells

Based on the blastocyst expansion and hatching status, blastocyst inner cell mass grading and trophectoderm grading, the embryo will be classified as a good-quality blastocyst if the grade is 3BB or above as illustrated in [Table 3](#).

**Table 3     Good-Quality Blastocysts**

3AA	4AA	5AA	6AA
3AB	4AB	5AB	6AB
3AC	4AC	5AC	6AC
3BA	4BA	5BA	6BA
3BB	4BB	5BB	6BB
	4BC	5BC	6BC
	4CA	5CA	6CA
	4CB	5CB	6CB
	4CC	5CC	6CC

The embryos on Day 5 will be summarised on both the embryo level and at the subject level.

### **Embryo Level**

At the embryo level all embryos evaluated will be included in the tables when reporting embryo stage and destiny of the embryo. For summary of blastocyst expansion and hatching status, blastocyst inner cell mass grading and trophectoderm grading all available embryo evaluations will be included. Frequency tables will be produced for the embryo stage, destiny, blastocyst expansion and hatching status, blastocyst inner cell mass grading and trophectoderm grading. These summaries will be obtained for the subjects in the mITT and ES cohorts.

## **Subject Level**

At the subject level the following will be derived for all subjects in the mITT and ES cohorts for the subjects that had oocytes retrieved:

- Number of blastocysts at Day 5
- Number of good-quality blastocysts at Day 5

These counts will be summarized using descriptive statistics of mean, median, SD, minimum and maximum.

### **9.5.6 Endometrial Thickness**

Endometrial thickness at the time of blastocyst transfer will be summarized for the mITT and ES cohorts.

## 10 Safety

### 10.1 General Considerations

Safety parameters will be evaluated for the ES and safety cohorts. Safety summaries will be presented by the 5 phases of the trial. These phases are defined as follows:

- Screening Phase: From the date of signing the informed consent through the day before the start of the oral contraceptive treatment.
- Suppression Phase: From the start of oral contraceptive treatment until the day before the start of the stimulation phase (start of MENOPUR treatment).
- Stimulation Phase: From the date of the first dose of MENOPUR through the day before the start of IMP.
- Treatment Phase: From the date of the first dose of IMP (PVR) through the end of the trial.
- Study Phase: From the date of the first dose of oral contraceptive through the end of the trial.

### 10.2 Adverse Events

Adverse events (AEs) are classified according to the latest available version of Medical Dictionary for Regulatory Activities (MedDRA).

Written narratives will be issued for all serious AEs (including deaths). Treatment-emergent AEs are AEs that occur during the *treatment phase* or a pre-existing medical condition that worsened in intensity during the *treatment phase*.

#### 10.2.1 Overview of Treatment-Emergent Adverse Events

A TEAE overview summary table will be prepared including the number of subjects reporting a TEAE, the percentage of subjects (%) with a TEAE, and the number of events (E) reported, for the following categories:

- Treatment-emergent adverse events
- Treatment-emergent Deaths
- Treatment-emergent Serious adverse events
- Treatment-emergent adverse events leading to withdrawal
- Treatment-emergent severe adverse events
- Treatment-emergent Adverse drug reactions

#### 10.2.2 Incidence of Adverse Events

Treatment-emergent adverse events will be summarised in a Table by SOC and PT of MedDRA using the latest available version. The Table will display the total number of subjects reporting an AE, the percentage of subjects (%) with an AE, and the number of events (E) reported. AEs will be

---

presented by system organ class (SOC) sorted alphabetically and preferred term (PT) sorted in decreasing frequency of occurrence.

Summary tables will be prepared for:

- All Treatment-emergent adverse events
- Treatment-emergent adverse events with an incidence [ $\geq 5\%$ ] of subjects in any treatment group
- Treatment-emergent adverse events by causality (related/unrelated)
- Treatment-emergent adverse events leading to death
- Treatment-emergent adverse events by intensity
- Treatment-emergent Serious adverse events
- Treatment-emergent Adverse events leading to withdrawal
- Non-serious treatment-emergent AEs with an incidence of at least 5%

Furthermore, the overall AE summary table by system organ class and preferred term will also be produced for the study phase, suppression phase, and the stimulation phase for the ES and safety cohorts.

Supporting data listings will be provided for:

1. All treatment-emergent adverse events sorted by centre and subject number
2. All treatment-emergent adverse events sorted by MedDRA System Organ Class and Preferred Term
3. Serious adverse events
4. Adverse events leading to death
5. Adverse events leading to withdrawal.

For listings specified in 3-5, there will be a variable that will indicate which phase of the trial each event occurred.

A separate AE listing will be provided for the screening phase, suppression phase, stimulation phase, and treatment phase of the trial.

### **10.2.3 Treatment-Emergent AEs of Special Interest**

Standardized criteria will be applied to some AEs of special interest to establish intensity/grade. For AEs associated with vaginal bleeding/spotting, vaginal pain and irritation, and vaginal or cervical abrasions and lesions, standardized criteria will be used by the sites to record the intensity of these AEs (Protocol Section 8). For these AEs and AEs associated with vaginal hemorrhage, vaginal infection and vaginal adhesions, a summary table of the treatment-emergent AEs of special interest will be produced by preferred term, grade (intensity), and seriousness for subjects in the safety cohort for the treatment phase and the study phase. These AEs will be identified using preferred terms.

### 10.3 Safety Laboratory Variables

Baseline for all laboratory analyses will be the values obtained at visit 4. If visit 4 is missing, then the last assessment prior to visit 4 will be used. Treatment-emergent laboratory data will include tests completed after the first dose of IMP through the residual time of drug effect. End of trial will include the last post-baseline observation during the trial.

Laboratory variables will be grouped under “Hematology”, “Clinical Chemistry” or “Urinalysis”.

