7.2.6 Clinical Laboratory Variables

The following laboratory tests will be performed:

- Screening and Visits 4, 9, and 10 (End-of-trial): serum chemistry: non-fasting glucose, blood urea nitrogen, creatinine, potassium, sodium, chloride, calcium, aspartate aminotransferase, alanine aminotransferase, and gamma-glutamyl transferase
- Screening and Visits 4, 9, and 10 (End-of-trial): hematology: red blood cell count, white blood cell count, hematocrit, hemoglobin, platelet count, and differential count
- Screening and Visits 9 and 10 (End-of-trial): urinalysis: specific gravity, ketones, pH, protein, blood, and glucose
- Screening: (prior to start of ovarian suppression): AMH
- Screening (Cycle Day 3 \pm 1 day): FSH
- Screening (Cycle Day 3 \pm 1 day) and Visits 1, 2, 4, and 5: serum estradiol
- Screening and Visits 6, 6P, and 7: β -hCG

- Visits 4, 5, 6, and 9: progesterone

The Investigator will review the laboratory results and evaluate and document whether the results are normal or abnormal and whether or not abnormal results are clinically significant. The laboratory report will be signed and dated by the Investigator. Results will be recorded in the subject's chart and eCRF.

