7.2.7 Vital Signs

Blood pressure, heart rate, and temperature will be measured at screening and Visits 3, 4, 5, 6, 7, 8, 9, and 10 (End-of-trial). Blood pressure and heart rate are to be measured while the subject is seated under resting conditions. All blood pressure measurements should be made using the same arm and prior to any scheduled blood draws.

The Investigator will review the vital sign results and evaluate and document whether the results are normal or abnormal and whether or not abnormal results are clinically significant. Results will be recorded in the subject's chart and eCRF.

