7.3.4 Height, Weight, and Body Mass Index Calculation

Height, weight, and body mass index (BMI) calculation will be performed at screening. In addition, weight and BMI will be assessed at Visit 9 and Visit 10. Results will be recorded in the subject's chart and eCRF.

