#### 10.3.5 Vital Signs

Baseline for all vital signs analyses will be calculated in the same manner as the safety laboratory variables in [Section 10.3](#). Treatment-emergent vital signs data will include tests completed after the

first dose of IMP through the end of the trial. End of trial assessment is defined to be the last post-baseline observation during the treatment phase of the trial.

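### Body weight is never scheduled at Visit 4, so its baseline falls back to screening and weight change before the first ring can create or mask a notable treatment-emergent flag

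*SAP*

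**What the plan says.** SAP 10.3 defines the laboratory baseline: "Baseline for all laboratory analyses will be the values obtained at visit 4". The fallback follows directly: "If visit 4 is missing, then the last assessment prior to visit 4 will be used". Urinalysis is named there as one of the three laboratory groups. SAP 10.3.5 carries the rule over: "Baseline for all vital signs analyses will be calculated in the same manner as the safety laboratory variables".

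SAP Appendix 1, Table 5 lists body weight among the notable vital-sign criteria. It has no absolute criterion value, only an increase or decrease of 7% or more from baseline. SAP 10.3.5.2 tabulates women with a normal baseline who have at least one notable treatment-emergent value.

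The protocol's schedules differ by variable:

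- Weight (Protocol 7.3.4) is taken at screening, and then: "In addition, weight and BMI will be assessed at Visit 9 and Visit 10". Protocol 6.3.8 makes the Visit 9 procedures apply to the Early-withdrawal visit as well.
- Urinalysis (Protocol 7.2.6): "Screening and Visits 9 and 10 (End-of-trial): urinalysis: specific gravity, ketones, pH, protein, blood, and glucose".
- Vital signs (Protocol 7.2.7): "Blood pressure, heart rate, and temperature will be measured at screening and Visits 3, 4, 5, 6, 7, 8, 9, and 10".

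The Visit 4 procedure list (Protocol 6.3.1) contains neither weight nor urinalysis.

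**The concern.** The fallback reads as cover for an occasional missed Visit 4 value. For blood pressure and pulse it works that way: if Visit 4 is missed, the Visit 3 value from one day earlier is available. For weight there is no Visit 4 value to miss. Unless an unscheduled weight exists, the fallback is the rule for every woman, and it reaches back to screening.

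Between that weight and the first ring lie any remaining screening time, the oral contraceptive, leuprolide, gonadotropin stimulation, the trigger and retrieval. Weight gained or lost over that sequence enters a count described as treatment-emergent. The blood pressure and pulse rows of the same table measure change from the day of the first ring, so one table covers different periods under one label.

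The trial has a single arm, so no control group shares the distortion. Abnormal vital-sign findings are a listed secondary endpoint, and Protocol section 2 says the trial will be judged on all the safety information together.

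**Working it through.** The documents give no screening-to-first-ring interval, so there is no stated figure to reproduce. It can be built from the protocol's limits.

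**Inputs**

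- Screening, S: up to 90 days from consent to the start of suppression (Protocol 6.1).
- Oral contraceptive, C: 14 to 21 days (Protocol Table 5-1).
- Leuprolide in down-regulation, L: 10 to 20 days, starting 4 days before the last pill (Protocol Table 5-1 and 6.1).
- Stimulation, M: at most 20 days (Protocol Table 5-1). No minimum is stated; I assume 5 days, the length of the initial fixed-dose period.
- Trigger to retrieval: 35-37 hours, taken as 2 days (Protocol 6.2.3).
- Retrieval to first ring: 1 day (Protocol 6.3.1).

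**Gap from screening weight to first ring** = S + C + (L − 4) + M + 2 + 1

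- Longest: 90 + 21 + 16 + 20 + 2 + 1 = 150 days.
- Shortest, assuming the screening weight is taken just before the first pill: 0 + 14 + 6 + 5 + 2 + 1 = 28 days.

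A day-by-day calendar count gives 148-149 and 26-27 days, so about 4 weeks to about 150 days is a fair summary.

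**Pre-ring share of the weight-change interval** = gap / (gap + days from first ring to the later weight)

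| Later weight | Days after first ring | Shortest gap | Longest gap |
|---|---|---|---|
| Visit 9 (day 70) | 70 − 1 = 69 | 28/97 = 29% | 150/219 = 68% |
| Visit 10 (day 84) | 84 − 1 = 83 | 28/111 = 25% | 150/233 = 64% |
| Stopped at Visit 6 (day 14), End-of-trial visit 2 weeks after last exposure | 13 + 14 = 27 | 28/55 = 51% | 150/177 = 85% |

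**Effect on the 7% rule.** If weight changes by a fraction x before the ring, the change r needed afterwards to reach the upper flag satisfies (1 + x)(1 + r) = 1.07. The values of x below are illustrative; the documents give no data on pre-ring weight change.

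- x = +3%: r = 1.07/1.03 − 1 = 3.9%
- x = +5%: r = 1.07/1.05 − 1 = 1.9%
- x = +7%: r = 0, so the threshold is met with no change on the ring
- x = −3%: r = 1.07/0.97 − 1 = 10.3%

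The distortion runs both ways: a pre-ring gain creates flags and a pre-ring loss masks them.

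**Urinalysis.** The schedule is the same, so the baseline is again screening. Tracing it through the SAP outputs:

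- 10.3.1 gives treatment-phase change from baseline for every laboratory variable, so it is affected.
- 10.3.2 specifies its shift tables for hematology and chemistry, which are measured at Visit 4, so they are not affected.
- 10.3.4 summarizes urinalysis values and abnormal counts by visit, without a baseline, so it is not affected.

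**The case against.** The best defence is that using the last pre-dose value is a common, pre-specified and reproducible rule, and that the SAP defines treatment-emergent data by timing after the first dose, without claiming attribution. Continuing women are also weighed at weeks 12 and 14 of pregnancy, so even a Visit 4 weight would not isolate an effect of the ring. All of this is fair and keeps the point small. It does not justify the label: the SAP nowhere says that the weight baseline is screening for everyone, and a reader of the table would assume the same baseline as in the rows above.

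Several stronger readings are tempting but not supported:

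- *The gap is typically 150 days.* That is the sum of every maximum; the documents give no typical value.
- *For a woman stopped at Visit 6, roughly 70-90% of the interval is pre-ring.* Ending the interval at Visit 6 gives 28/41 = 68% to 150/163 = 92%, but no weight is scheduled at Visit 6. Those figures would fit only an Early-withdrawal weight taken that same day. The last observation is the End-of-trial visit, which gives 51-85%.
- *Temperature is part of the contrast.* Table 5 gives temperature no change criterion, so the contrast is with blood pressure and pulse only.
- *Urinalysis is as badly affected as weight.* It has no notable-value flag, and only the general change statistics are touched.
- *Every woman with a 7% pre-ring gain will be counted.* The table requires a normal baseline, and the SAP gives no normal range for weight, so who enters that row is undefined.

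It is also true that Protocol 7.2.7 does not include weight among vital signs. Weight enters that display only through SAP Table 5.

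**Conclusion.** The concern holds for body weight. Followed as written, the SAP measures notable weight change from screening, about 4 weeks to at most about 150 days before the first ring, and reports it as treatment-emergent. Suppression and stimulation always fall inside that interval. The pre-ring share is about 25-64% for women reaching Visit 10 and about 51-85% for a woman stopped at Visit 6 who attends End-of-trial.

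These ranges rest on the protocol's limits, nominal visit days, an assumed 5-day minimum stimulation and no unscheduled weight before Visit 4. The number of women whose flag would change cannot be estimated from the documents. For urinalysis the problem is confined to SAP 10.3.1. This is a minor correction to a secondary safety display; the primary endpoint and its comparison with 15% are unaffected.

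**What to change.** In SAP 10.3 and 10.3.5, limit the Visit 4 baseline and the description treatment-emergent change to variables measured at Visit 4: chemistry, hematology, blood pressure, heart rate and temperature. Keep the fallback for genuinely missing values of those variables.

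Take body weight out of the notable treatment-emergent count in SAP 10.3.5.2. Report it in a separate display as change from screening over the study phase, keeping the 7% criterion if wanted, and drop the normal-baseline condition for it. In SAP 10.3.1, label any urinalysis change as change from screening.

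The cost is SAP wording and table labels, with no new data and no change to the visit schedule. The trial then makes no ring-specific statement about weight, which its measurements could not support in any case.

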#### 10.3.1 Summary Statistics

For treatment phase of the trial, for the safety cohort, mean change and mean percentage (%) change from baseline at end of trial will be presented for each laboratory variable. In addition, descriptive statistics, i.e., the number of subjects with data, mean (standard deviation), median, minimum, and maximum values, will be presented for observed values and change from baseline at each time-point for each laboratory variable. The screening value will also be summarized for both the safety and the ES cohorts.

#### 10.3.2 Laboratory Variable Shift Tables

Changes relative to normal ranges are presented with shift tables with total number of subjects, and number and percent of subjects who experienced a shift from baseline to their end of trial visit. The following categories for shift tables are defined:

- Low: Values which are below the lower reference range limit;
- Normal: Values which are within the lower and upper reference range;
- High: Values which are above the upper reference range limit.

For all hematology and clinical chemistry variables, shift tables will be prepared to show all shifts. More specifically, for hematology and clinical chemistry, tables presenting the changes from *Low* or *Normal* to *High* and from *High* or *Normal* to *Low* will be provided.

#### 10.3.3 Data Listings

Data listings will be prepared for all subjects with any abnormal laboratory value at any time-point (including screening, baseline).

#### 10.3.4 Urinalysis

Urinalysis parameters will be summarized by visit for the ES and safety cohorts. For continuous variables, mean, standard deviation, median, minimum and maximum will be used to summarize the assessment. In contrast, for categorical parameters, percentages and frequencies will be used. Furthermore, for each urinalysis parameter the number of subjects with abnormal laboratory values will be summarized by visit for the ES and safety cohorts.

#### 10.3.5 Vital Signs

Baseline for all vital signs analyses will be calculated in the same manner as the safety laboratory variables in [Section 10.3](#). Treatment-emergent vital signs data will include tests completed after the

first dose of IMP through the end of the trial. End of trial assessment is defined to be the last post-baseline observation during the treatment phase of the trial.

